### B1. PURPOSE OF PROTOCOL

The purpose of the protocol is to test the hypothesis that elimination of the use of non-depolarizing neuromuscular blocking agents (NMBA) for maintenance of general anesthesia in patients at high risk of developing postoperative pulmonary complications (PPCs) undergoing non-cardiac operations is associated with reduced risk of PPCs.

*Specific Aim 1:* To test the primary hypothesis that avoidance of non-depolarizing NMBAs, as compared to standard care which includes the use of non-depolarizing NMBAs, is associated with a lower risk of a composite of PPCs (including respiratory failure, suspected respiratory infection, aspiration pneumonia or pneumonitis, atelectasis, bronchospasm and reintubation within 28 days of index operative procedure) and all cause in-hospital mortality both within 28 days of index operative procedure.

*Specific Aim 2:* To test the key-secondary hypothesis that avoidance of non-depolarizing NMBA, compared to standard care which includes the use of non-depolarizing NMBA, is associated with higher vasopressor equivalent dose, which may be the consequence of higher dosing of opioids and anesthetics. Further, we shall also evaluate the following secondary endpoints: duration of intraoperative hypotension (defined as mean arterial pressure <55mmHg), surgeon's assessment of surgical field, cost of anesthetic medications, time to PACU discharge readiness (interval between arrival and time when meeting PACU discharge criteria), rate of unplanned ICU admissions or return to operating room within 24 hours, hospital length of stay and 30-day readmission rates.

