### Study Endpoints:

1. Primary Endpoint: Composite of postoperative pulmonary complications (respiratory failure, suspected respiratory infection, aspiration pneumonia or pneumonitis, atelectasis, bronchospasm and reintubation) and all cause in-hospital mortality both within 28 days of index operative procedure
2. Secondary endpoint (safety):
  - a. Vasopressor use between groups,
  - b. Duration of intraoperative hypotension (defined as mean arterial pressure <55mmHg),
  - c. Surgeon's assessment of surgical field.
3. Other end points:
  - a. Time to post-anesthesia care unit (PACU) discharge readiness,
  - b. Cost of anesthetic medication,
  - c. Rate of unplanned ICU admission or return to operating room within 24 hours,
  - d. Hospital length of stay
  - e. 30-day readmission rates.

The following baseline variables will also be collected: Clinical and demographic variables will be collected including age, gender, body mass index, type and severity of chronic lung disease, ASA class, obstructive sleep apnea, use of CPAP/Bipap, smoking history, hypertension, coronary artery disease, heart failure, cerebrovascular accident or neurologic dysfunction, history of aspiration, use of home oxygen, chronic kidney disease, diabetes mellitus, Charlson comorbidity index and Procedural Severity Score. Additionally, to track other important intraoperative and postoperative

factors related to overall patient outcome and protocol adherence, we will record administrative, demographic, clinical and billing data including:

- Vital Signs
- Medications administered
- Ventilator settings
- Urine output
- End tidal carbon dioxide concentration
- Dead space ventilation
- Alveolar-Arterial oxygen gradient
- Blood transfusion history
- Length of operation
- Type of operation

*Assessment of Primary Outcome:*

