## 1. STATISTICAL CONSIDERATIONS

- a. **Sample Size Justification:** Assuming the incidence of PPC to be 40% and 15% in Groups C and NR, respectively, we estimated that we would need at least 50 patients in each group to achieve a two-sided  $\alpha = 0.05$  and 80% power. Although the effect size in this assumption is high, if a difference of this magnitude is observed, the study will be well-powered. However, due to the scant knowledge about the directionality of the effect that we are exploring, observing even a smaller difference in this preliminary study will be useful in estimating a reliable effect size that can be used in designing a larger, more definitive study in the future. Results from our secondary endpoints will provide valuable exploratory data on the safety and efficacy of maintenance of general anesthesia without non-depolarizing NMBA.
- b. **Data Analysis:** Descriptive statistics will be assessed and presented as mean( $\pm$ -SD), median(IQR) or frequencies and proportion depending on type and distribution. Differences between groups in continuous variables will be compared using parametric or non-parametric tests as appropriate. Categorical data including the primary outcome (composite of PPC and all cause 28 day in-hospital mortality) will be compared with Chi-square or Fisher's exact test as appropriate. Two-sided p-value of less than 0.05 will be considered significant for all analyses. Logistic regression will be used to assess the relationship between the composite outcome and use or avoidance of non-depolarizing NMBA. Data will be presented as odds ratio and 95% confidence intervals. Individual outcomes will be reported to demonstrate potential trends between the two groups. Continuous outcome variables will be compared between treatment groups using t-test or Wilcoxon rank sum test as appropriate. Exploratory sensitivity analyses will be conducted to analyze if treatment effects were moderated by study site, surgical site or preoperative risk score after adjusting for patient and procedural risk factors such as Charlson comorbidity index and Procedural Severity Score. Statistical consultation shall be provided by [name], PhD at MGH. Statisticians will be blinded to group assignment.

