### Exclusion criteria:

1. Emergency surgery
2. Ambulatory (outpatient) surgery
3. Scheduled for elective postoperative ventilation
4. Planned return to operating room within 7 days of index procedure
5. Exposure to general anesthesia within 7 days prior to planned procedure
6. Requirement mechanical ventilation at baseline (not including stable use of CPAP/BiPAP)
7. Pregnant patients: as detected by patient self-reporting or diagnosed by preoperative pregnancy testing according to institutional policies at BIDMC and MGH
8. Allergy to either non-depolarizing muscle relaxants or sugammadex

9. Clinician refusal
10. Prisoner

*Women of childbearing potential:*

Women of childbearing potential will be eligible for enrollment in this study. Preoperative pregnancy testing will take place according to the current BIDMC/MGH (as applicable) surgery and anesthesia guidelines. No additional serum or urine pregnancy test(s) will be performed for research purposes. Subjects will be excluded from participation if they are pregnant.

*Gender and Racial Distribution of Subjects:*

We anticipate that our study population will reflect the normal distribution of race and gender of patients presenting for non-cardiac surgeries at MGH and BIDMC

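### Time to PACU readiness is undefined for patients diverted or dying before readiness, and death cuts hospital stay short; the plan has no scoring rule for either

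*Combined protocol and SAP*

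**What the plan says.** Section B1, Specific Aim 2, gives the only definition of the PACU outcome: "time to PACU discharge readiness (interval between arrival and time when meeting PACU discharge criteria". It needs both an arrival and a time at which criteria are met. The same sentence ends with "hospital length of stay and 30-day readmission rates", without a start, an end or a rule for death.

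The Study Endpoints list places "Time to post-anesthesia care unit (PACU) discharge readiness" and "Hospital length of stay" in its third tier, other end points, together with 30-day readmission. Specific Aim 2 calls the same measures secondary. The list also shows that the interrupting events are foreseen: the primary composite includes "all cause in-hospital mortality both within 28 days of index operative procedure", and a separate endpoint is "Rate of unplanned ICU admission or return to operating room within 24 hours".

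Section 1, Statistical Considerations, Data Analysis, states: "Continuous outcome variables will be compared between treatment groups using t-test or Wilcoxon rank sum test as appropriate". No section says how to score a patient with no PACU interval or a patient who dies in hospital. There is no worst rank, competing-risk method, alive-and-out-of-hospital measure or missing-data rule for these endpoints.

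Among the exclusion criteria is "Scheduled for elective postoperative ventilation". Planned ICU care without ventilation is not excluded.

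**The concern.** Who has a PACU time is decided after randomisation. A patient kept intubated and taken to ICU, or moved from PACU to ICU or theatre before meeting criteria, has no value, and the reason is often a poor course. The population makes this plausible: entry requires a score of at least 20, for which Table 1 gives a predicted risk of 35.4%, and the high-risk services include thoracic, vascular, transplant and neurosurgery. The anesthesia team knows the allocation, and postoperative care is left to the clinical teams, so destination could depend on arm.

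Hospital stay has a different problem. A value exists, but for a death it reflects only when the patient died. A death on day 3 enters a t-test or Wilcoxon test as a better result than a survivor discharged on day 6. For readmission, a patient who dies before discharge is not at risk.

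What is at stake is the reading of three supporting outcomes. Section B4 names shorter stay as a possible benefit, and the trial is meant to inform a larger one, which could inherit the definitions.

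**Working it through.** **Inputs from the documents.** 1:1 allocation, at least 50 per group, and two-sided 0.05 for all analyses. No figure is given for PACU time, stay, ICU bypass or mortality, so every rate below is an assumption.

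**The plan's own figure.** The only number borrowed is 50 per group, from 40% against 15% on the primary composite. With pooled variance, n = [1.960·√(2·0.275·0.725) + 0.842·√(0.40·0.60 + 0.15·0.85)]² / 0.25² = 48.9, so 49 per group; power at 50 is 80.9%. The stated size reproduces and is not in question.

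**Step 1. PACU time, ranking failures worst.** Let a and b be the proportions failing to reach readiness in the two arms, with times otherwise equal. The probability that a patient from the first arm does worse is

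P = a(1−b) + 0.5ab + 0.5(1−a)(1−b) = 0.5 + (a−b)/2.

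- a = 0.10, b = 0.02: 0.098 + 0.001 + 0.441 = 0.54.
- a = 0.15, b = 0.05: 0.55.
- Complete cases in either setting: 0.50.

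The null standard error at 50 per arm is √(101/(12·50·50)) = 0.058. The shifts are 0.04/0.058 = 0.7 and 0.05/0.058 = 0.9 standard errors, giving roughly 10% to 14% power.

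**Step 2. PACU time when the slowest patients are the ones lost.** Assume log-normal times with median 90 minutes in NR (log-SD 0.6) and 1.2 times as long in C, so true medians are 108 and 90. Remove the slowest fraction of each arm. This is an extreme form of selection.

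| Lost, C / NR | Observed medians, C / NR | Difference (true: 18) |
|---|---|---|
| 10% / 10% | 100.2 / 83.5 | 16.7 min |
| 20% / 10% | 92.9 / 83.5 | 9.4 min |
| 30% / 10% | 85.8 / 83.5 | 2.3 min |

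Unequal loss shrinks the difference; in these cases it does not reverse it.

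**Step 3. Hospital stay.** Simulation, 50 per arm, survivors' stay identical in both arms (log-normal, median 6 days, log-SD 0.7), deaths uniform over days 1–3 or days 5–28. At 2% to 6% mortality, 1 to 3 of 50 patients per arm die.

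| Deaths, C / NR | Days of death | Mean stay, C − NR | P(C shorter), as recorded | P(C better), death worst |
|---|---|---|---|---|
| 2% / 2% | 1–3 | +0.02 | 0.500 | 0.501 |
| 2% / 2% | 5–28 | +0.04 | 0.499 | 0.499 |
| 4% / 0% | 1–3 | −0.25 | 0.519 | 0.482 |
| 4% / 0% | 5–28 | +0.39 | 0.485 | 0.479 |
| 6% / 2% | 1–3 | −0.20 | 0.515 | 0.478 |
| 6% / 2% | 5–28 | +0.35 | 0.485 | 0.480 |
| 10% / 4% | 1–3 | −0.34 | 0.526 | 0.471 |
| 10% / 4% | 5–28 | +0.53 | 0.479 | 0.470 |

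Early deaths make the arm with more deaths look better. Late deaths do not. Equal mortality gives no material bias.

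**The case against.** Several stronger readings are tempting, and the documents do not support them.

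- *Neither measure has a usable value for any patient who goes to ICU or dies.* A patient who goes straight to ICU and survives has an ordinary length of stay. One who dies after meeting PACU criteria has an ordinary PACU time. A patient reintubated in PACU may meet criteria later, and a return to theatre within 24 hours may follow readiness.
- *Every death counts as a short stay.* Mortality is followed to 28 days, and a late death gives a long stay.
- *The PACU comparison favours the arm with more failures.* Complete cases in Step 1 give 0.50, which favours neither arm; a disadvantage is hidden or diluted.
- *The trial expects arms to differ in death and ICU admission.* The sample-size section assumes a difference in pulmonary complications only and says little is known about direction. Section B4 mentions mortality and ICU admission only as possible consequences.
- *The plan prescribes these results.* It is silent; they are what the stated tests give by default. The readmission denominator is not stated and could be patients discharged alive.

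The best case for leaving the plan alone is that the bad outcomes are not lost. Death and reintubation are in the primary composite, unplanned ICU admission has its own endpoint, and individual outcomes are to be reported. The exclusions of emergency surgery, planned return to theatre within 7 days and baseline ventilation also reduce the number of such cases. These points stand and lower the importance. They do not supply a value for the PACU interval, nor stop a death from shortening a stay.

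**Conclusion.** The gap is real and modest. PACU time is missing for patients who bypass the PACU or whose course is interrupted before readiness, and the planned test silently leaves them out. Hospital stay treats death as discharge, so its direction depends on when deaths occur. Readmission ignores that the dead cannot be readmitted. Bias arises only if these events differ by arm. Its size cannot be fixed from the documents, and on the assumed rates it is small beside the sampling error at about 50 per arm: a shift of 0.04 to 0.05 in the Mann-Whitney probability against a standard error of 0.058, or a few tenths of a day in mean stay. The larger loss in Step 2 needs strongly selective and unequal bypass. With these measures in the lowest endpoint tier of a pilot, this is a cheap improvement of low priority. It does not threaten the primary analysis.

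**What to change.** Before unblinding, add a scoring rule for each endpoint.

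- **PACU time:** use the Wilcoxon test already allowed, with unplanned ICU transfer, return to theatre or death before readiness ranked worst. Leave out only patients whose ICU destination was recorded before randomisation, so that the omission cannot depend on arm.
- **Hospital stay:** give in-hospital deaths the worst rank in the Wilcoxon test. Days alive and out of hospital is a reasonable alternative, but it changes the endpoint.
- **Readmission:** report 30-day readmission or death beside readmission, and state the denominator of each.
- **Counts:** give the number of patients scored by each rule, by arm.

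The cost is endpoint wording and one baseline field for planned destination; no extra patients are needed. In-hospital deaths to day 28 are already collected. Deaths after discharge, or on days 29 and 30, would need ascertainment if the composite is to cover the full 30 days. The downside is that a ranked result is less direct to read than minutes or days; medians among patients with an observed value can be shown descriptively beside it.

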### B2. SIGNIFICANCE AND BACKGROUND FOR THE STUDY

[figure not shown]
#### **Importance:**

The need for safe anesthesia practices is growing in parallel with global surgical volume. Non-depolarizing NMBA are commonly used as part of 'balanced anesthesia techniques'. Though helpful in facilitating endotracheal intubation and optimizing surgical conditions, their use has been strongly associated with higher risk of postoperative complications. Large retrospective registry studies have consistently shown non-depolarizing NMBA use to be associated with increased risk of PPCs, hospital length of stay, overall costs and 30 day unplanned readmission rates. Overall, this may translate not only into significant *potentially avoidable* patient morbidity but also in substantial healthcare expenditure considering their widespread use.

#### **Residual neuromuscular blockade and postoperative pulmonary complications: Incidence and proposed mechanisms**

A recently published prospective cohort study from a US cohort estimated the incidence of residual neuromuscular blockade post-extubation at >60%. Volunteer studies have demonstrated that even minimal residual neuromuscular blockade in the absence of anesthetics significantly impairs genioglossus muscle activity and thereby predisposes the patient to upper airway collapse. Residual blockade leads to delayed initiation of swallowing, pharyngeal dysfunction, and incoordination thereby significantly increasing risk of aspiration risk. Although these factors are recognized as the

primary drivers of increased risk of PPC in patients with residual neuromuscular blockade, other factors contribute as well. **Figure 1** summarizes the multiple pathophysiological mechanisms which increase the risk of adverse pulmonary complications in patients with residual paralysis.

**Figure 1:** Pathophysiological mechanisms of residual neuromuscular blockade contributing to pulmonary complications. Impairment of the upper airway dilator muscle tone at even at minimal levels of residual neuromuscular blockade represents a key element that increases the vulnerability to aspiration, and negative pressure pulmonary edema. Avoidance of non-depolarizing NMBA may eliminate these mechanisms of postoperative respiratory complications.

### Problems associated with reversal of neuromuscular blockade (NMB)

Counter-intuitively, observational studies indicate that antagonism of NMB with acetylcholinesterase inhibitors does not completely mitigate the risk of PPC, and can, paradoxically increase the risk of respiratory complications, which may be in part explained by depolarizing neuromuscular blockade. In healthy volunteers, usual reversal dosage of neostigmine and glycopyrrolate given after complete recovery from NMB impairs upper airway dilator volume genioglossus muscle and diaphragmatic function, as well as skeletal muscle strength thereby predisposing patients to respiratory complications. Although sugammadex is able to reverse various degrees of neuromuscular blockade quicker and has a better safety profile compared to neostigmine, its use does not completely mitigate the adverse effects of residual NMBA.

### Inappropriate management of non-depolarizing neuromuscular blocking agents (NMBA)

Despite having been in clinical use over decades, significant practice variability exists among practitioners surrounding the use of NMBAs. Mirroring these observations, the recently published POPULAR study reported only about half of patients receiving NMBA were reversed, and a third were extubated at TOF-ratio<0.9 in contrast to established best practices. Recent data show that the vast majority of anesthesiologists are *overconfident* in their ability to manage neuromuscular blockade, which likely contributes to the overwhelming belief that neuromuscular blockade could be managed intuitively without use of any objective neuromuscular monitoring. This variability in provider practices is unsurprising, given that international societies are inconsistent in their guidelines. While few international societies advocate using some form of neuromuscular monitoring

when using non-depolarizing NMBA; only the Czech Society of Anesthesiologists explicitly recommends the use of quantitative monitoring and a TOF%>0.9 as adequate recovery. Notably the American Society of Anesthesiologists' guidelines on standards of basic anesthetic monitoring is silent on this topic [Accessed at [asahq.org](http://asahq.org)]. Thus, we expect that even during the proposed study, many anesthesia providers will not use NMBA appropriately - a trend noted in multiple observational and randomized control trials including our own work. We do not wish to standardize the use of NMBA in the control arm since we think both intrinsic side-effects as well as consequences of their inappropriate clinical use of NMBA affect patient safety.

### **Beneficial effects of NMBA**

NMBA dose-dependently improve surgical conditions, and some authors conclude that deep NMB is associated with better operating conditions during specific types of surgery. However, use of these agents is not an *absolute* requirement to achieve optimal conditions. In a double-blinded placebo-controlled RCT of patients undergoing prostatectomy under general anesthesia, only 24.5% of patients required a "rescue" NMBA in the placebo arm and good-to-excellent surgical conditions were achieved in 2/3 of patients in the placebo arm^15. Inhaled anesthetics, opioids, and neuraxial analgesia can produce dose-dependent relaxation of skeletal muscles such that non-depolarizing NMBA may not be required to optimize surgical conditions. This protocol proposal also allows for rescue NMBA as needed.

In the intensive care unit, early use of NMBA in patients with severe ARDS has shown some benefits, probably by a reduction in patient-ventilator asynchrony. Although patient-ventilator dyssynchrony might be an issue in the operating rooms as well there are other medications which could be used to alleviate this issue successfully. The results of the recently concluded NIH-funded ROSE (Reevaluation of Systemic Early Neuromuscular Blockade) trial which our institution has contributed to, may even challenge the assumption of beneficial effects of NMBA.

### **Significance**

More than 400 million people receive NMBAs annually, either in the operating theater or in the ICUs. Use of non-depolarizing NMBAs during anesthesia is associated with an increased risk of clinically meaningful respiratory complications. Excellent surgical conditions can be achieved without the use of NMBA in patients undergoing a wide range of procedures including spine and prostate surgery. Whether avoidance of non-depolarizing NMBA can mitigate the adverse postoperative risks associated with standard management of NMB is unclear in the absence of randomized controlled trials examining the consequences of use of non-depolarizing NMBA on PPC. Knowledge from this trial will help practitioners decide whether the elimination of NMBA may be a useful strategy to achieve better postoperative respiratory outcomes in patients at high risk of postoperative respiratory complications. The use or avoidance of non-depolarizing neuromuscular blockade agents to maintain general anesthesia and achieve optimal surgical conditions is accepted as the standard of care at both clinical centers regardless of patient participation in this study. Therefore, in addition to providing pilot data for a larger definitive trial, our results are likely to have an impact on the discussion of safety strategies to achieve optimal surgical conditions with and without NMBA.

### **Preliminary studies**

Our study is aimed at patients with high pre-test probability of developing PPCs. In order to identify such patients preoperatively we developed a risk prediction score (**Table 1**) using data from all patients who underwent non-cardiac procedures under general anesthesia with endotracheal intubation at MGH and BIDMC between 2007-2015. 12.2% patients developed PPC (defined as a composite of reintubation within 7 days and respiratory failure, respiratory infection, bronchospasm, atelectasis, pleural effusion, aspiration pneumonitis, pneumothorax within 28 days). Our risk prediction-model which we developed using our published standards demonstrates good discrimination (AUROC of 0.84). We plan to use this prediction instrument along with expanded definition of high risk surgical services as defined by well validated SPORC score (vascular,

transplant, neurosurgery, thoracic, general and burn surgery) and physician review of electronic health records to determine “high risk surgery” to screen for eligibility. **Table 2** shows the predicted incidence of PPC in different risk subgroups of patients (MGH and BIDMC) in an 18-month period.

Risk Prediction Score		Estimated Risk of outcome	
High-risk surgery*	13	Score Point Value	Probability of Outcome (%)
Inpatient surgery	11		
Pneumonia within 1 month	8	0	0.2
ASA $\geq 3$	3	5	0.9
Age $\geq 80$	2	10	3.5
Duration of surgery > 3 hours	2	15	12.3
History of heart failure within 1 year	2	20	35.4
Alcohol abuse within 1 year	1	25	68.2
Home oxygen therapy	1	30	89.3
BMI < 18.5 kg/m 	1	35	97.0
Chronic pulmonary disease within 1 year	1	40	99.2
Total points	44	44	99.8
*ENT, thoracic, vascular, transplant, neurosurgery, thoracic, general, and burn surgery			

\*The expanded definition of high risk surgical services as defined by SPORC score includes vascular, transplant, neurosurgery, thoracic, general and burn surgery.

**Table 1:** Risk prediction tool and estimated risk of outcomes. Logistic regression was used to build a model including all candidate predictors. Stepwise elimination was performed with a  $p = 0.01$  for retaining in the model. Individual weighting values were determined by dividing the respective beta coefficient by the overall smallest beta coefficient of all predictor variables. Rounded to the nearest integer, the score point values were multiplied by the corresponding predictors, thus estimating the final prediction instrument.

Risk category for postoperative respiratory complications	Predicted numbers of patients that can be recruited for the study within 18 months n (%)
<10%	47,175 (78.2)
$\geq 10\%$ and <20%	8,519 (14.1)
$\geq 20\%$ and <30%	1,599 (2.6)
$\geq 30\%$ and <40%	288 (0.5)
$\geq 40\%$ and <50%	215 (0.4)
$\geq 50\%$	2,567 (4.3)
Total number of patients	60,362 (100)

**Table 2:** Predicted number of patients in different risk categories that can be recruited within 18 months at MGH and BIDMC

